3.2 Study Visits and Phone Contacts

346 Participants will have a phone (or video-conference) follow-up visit at 3 days, 1 week and 3 weeks, a
347 clinic follow-up visit at 6 weeks, a phone follow-up visit at 9 weeks, and a final clinic visit at 13 weeks,
348 within the windows specified below.

TARGET DAY/WEEK	VISIT OR PHONE	TARGET WINDOW (AROUND TARGET DAY/WEEK)
3 days	P	± 1 day
1 week	P	± 2 days
3 weeks	P	± 7 days
6 weeks	V	± 7 days
9 weeks	P	± 7 days
13 weeks	V	91-98 days

349 If necessary, visits should be completed out-of-window rather than missed. A visit is not considered
350 missed until the next visit/phone window opens.

351 The goal will be for all participants to complete all scheduled visits. However, participants who
352 (because of unforeseen circumstances or due to changes in contact precautions that may be needed
353 during the evolving COVID-19 pandemic) are unable or unwilling to return for all follow-up visits
354 will be permitted to return for key visits only (screening visit, device training visit) as an alternative to
355 withdrawal from the study. Remote (phone) visits will still be performed as scheduled. When a participant
356 is placed into this status, remote visits will not be recorded as protocol deviations.

357 Additional phone and office visits may occur as needed.

358 For the 6 and 13 week visits, if a clinical site believes these visits need to be performed remotely, the
359 following approvals must be obtained prior to conducting the visit remotely:

- Sponsor approval for the reason the visit cannot be performed in person
- Investigator approval at the site level for the reason the visit cannot be performed in person

362 In addition, all study procedures listed in section 3.2.1 are to be completed, including upload of the study
363 device and review of the device data. If the final visit is performed remotely, participant will mail in the
364 A1c kit from home and mail back the study devices to the study site.

3.2.1 Procedures at Study Visits

366 The following procedures will be performed at each visit, unless otherwise specified:

- Review of study device data
- Assessment of compliance with study device use by review of any available device data
- Assessment of device issues that have occurred
- Assessment of adverse events, using open ended questions to capture hyperglycemic and hypoglycemic events, and their underlying cause and relationship to the study device or other parts of the system (such as the infusion set).

373 At 13 weeks (or if at subject withdrawal), the study staff will then supervise the participants transition
374 back to their standard of care therapy as follows:

375 • Study staff will re-evaluate the subject's baseline therapy doses, noting changes in basal rates,
376 carbohydrate ratios, and correction factors in use at the end of the trial.

377 • The study investigator will supervise and confirm the entry of settings in the insulin delivery profile
378 of the participant's home pump at the end of the study.

379 • Blood draw (venipuncture or fingerstick) for HbA1c measurement at central lab (Device Training
380 Visit and 13 weeks only)

381 **3.2.2 Unscheduled Visits**

382 Participants may have unscheduled visits during the study period if required for additional device training
383 or other unanticipated needs per the study investigator discretion. Study participants will be instructed to
384 upload their study device any time the participant changes device profile settings, and study staff will
385 document review of these changes as an unscheduled visit. Documentation of the review must occur as an
386 unscheduled visit if these changes are not being performed in window/part of the scheduled study visits
387 and are not captured as part of a scheduled study visit.

388 **3.2.3 Exercise and Meal Challenges**

389 Participants will complete 3 meal and 3 exercise challenges during the study. Procedures are described in
390 section 5.1.

391 **3.3 Early Discontinuation of Study Device**

392 Participants who discontinue the study device prior to 13 weeks, either by choice or by investigator
393 decision, will be asked to come for an end of study visit and then will be dropped from the study.
394 If the visit occurs at 6 weeks or after, blood will be drawn for the central laboratory HbA1c measurement.

396

Chapter 4: Study Devices and Drugs

397

4.1 Study Devices

398

The investigational device (CLC system) includes an insulin pump and a continuous glucose monitor.

399

4.1.1 Insulin Pump

400

The study system will include the Tandem t:slim X2 with Control-IQ 1.5 technology.

401

4.1.2 Continuous Glucose Monitoring

402

The study CGM that is part of the CLC system is the Dexcom G6, which includes a transmitter and sensors. The CGM sensor will be replaced at least once every 10 days.

404

4.1.3 Blood Glucose Meter

405

The study blood glucose meter is the Contour® NEXT (Ascencia Diabetes Care).

406

Blood glucose levels will be measured using the study's blood glucose meter (glucometer) and the CGM device will be calibrated if needed using the study glucometer and strips in accordance with the manufacturer's labeling.

409

4.1.4 Ketone Meter

410

The study blood ketone meter is the Precision Xtra Blood Glucose and Ketone Monitoring System (Abbott Diabetes Care).

412

Blood ketone levels will be measured when needed to evaluate prolonged hyperglycemia. The blood glucose meter component of the Precision Xtra device will not be used.

414

4.2 Study Device and Drug Accountability Procedures

416

Device accountability and inventory will be documented to include detailed inventory records of the study study CGM supplies, and Tandem insulin pump system.

418

4.3 Participant Access to Study Device at Study Closure

419

Participant will return all investigational study devices and supplies (insulin pump, CGM and related supplies) at study closure. Participant may keep the study ketone meter and study glucometer if these devices are not marked for investigational use only.

422 Chapter 5: Testing Procedures and Questionnaires

423 5.1 Meal and Exercise Challenges

424 Participants will complete 3 meal and 3 exercise challenges with the study device.

425 A minimum of 48 hours will occur between all challenges for each participant. Challenges may be
426 performed in any order.

427 Participants will be instructed to communicate with study staff within one day prior to each challenge to
428 review procedures and to have a contact with study staff after the completion of each challenge.

429 Hyperglycemia and Hypoglycemia treatment guidelines (sections 3.1.3 and 3.1.2) remain in effect for the
430 challenges, and will be reviewed with participants prior to each challenge.

431 Participants will be reminded they must have a care partner, trained in these hypoglycemia and
432 hyperglycemia treatment guidelines, present during the challenges and overnight until 6 AM the next day.

433 Site staff will directly contact the participant if they do not receive a follow up contact from participants
434 when 24 hours have passed since the time of completion of the planned challenge.

435 5.1.1 Meal Challenges

436 The same meal should be used for each of the three meal challenges—either lunch or dinner (participant
437 choice).

438 During study device use, the three meal challenges will consist of:

- 439 • No bolus for the meal
- 440 • 50% bolus - calculate the bolus dose using the bolus calculator, and deliver half the
441 recommended dose of insulin.
- 442 • Full bolus for the meal based on calculated bolus dose using the bolus calculator.

443 For each meal challenge, participants will:

- 444 1. Be in a fasting state for two hours prior to consuming the meal and the last manual insulin bolus
445 more than two hours prior to the meal.
- 446 2. Only begin the meal challenge if CGM glucose is between 70 mg/dL and 200 mg/dL. *Subjects
447 with hyperglycemia > 200mg/dL will reschedule their challenge for another time. If < 70 mg/dL,
448 carbohydrate treatment can be given, after which the meal challenge can continue.*
- 449 3. Consume at least 50 grams carbohydrate for the meal. *Each participant will use the same meal
450 for all of their meal challenges in the study. Participants will be encouraged to use the same
451 frozen entrée of their choice for consistency.*
- 452 4. Write down the start and end time of eating the meal, as well as the meal content (to include
453 amount of carbohydrate, protein and fat) on the study provided logbook.
- 454 5. Not give an additional bolus for up to 3 hours after the meal challenge, unless BG is above 300
455 mg/dL for more than 1 hour, or symptoms of hyperglycemia develop.
- 456 6. Not take additional carbohydrates for up to 3 hours after the meal challenge, unless BG is < 70
457 mg/dL, or symptoms of hypoglycemia develop.
- 458 7. Not exercise for 3 hours after the meal challenge.
- 459 8. After the meal is completed, perform an SMBG (fingerstick) glucose check 1 hour after, prior to
460 bed, and once overnight.

461 9. Notify the site within 24 hours after completion of each meal challenge.
462 10. The meal challenge will end 3 hours after the meal is completed.

463 **5.1.2 Exercise Challenges**

464 For each exercise challenge, participants will:

465 1. Have extra carbohydrate containing snacks and glucagon on hand during and after exercise.
466 2. Per their usual routine and investigator guidance, consider activation of “exercise activity” on the
467 pump up to 45 minutes ahead of actual exercise, to allow for less insulin on board when starting
468 exercise.
469 3. Consider reducing the last meal bolus prior to exercise as a way to reduce insulin on board and
470 limit hypoglycemia.
471 4. Perform one hour of exercise, including at least half an hour of moderate activity. Exercise does
472 not need to be the same activity each time.
473 5. Only begin exercise if CGM glucose is ≥ 120 mg/dL and CGM glucose is not trending
474 downward.
475 6. Write down the start time of last meal and amount and time of last insulin dose, type of exercise
476 performed, as well as the start and stop time of each exercise session in the study logbook (*as this*
477 *may not correlate exactly with exercise activity use on the pump*). Participants may take breaks if
478 needed, as long as the full hour of activity is completed.
479 7. Stop the exercise challenges at any point for injury or development of new symptoms;
480 development of chest pain/pressure, feeling unwell, development of hypoglycemic symptoms,
481 undue shortness of breath, signs of poor perfusion (leg pain/claudication), or for any other reason.
482 8. After the exercise challenge is completed, perform an SMBG (fingerstick) glucose check 1 hour
483 after, prior to bed, and once overnight.
484 9. Notify the site within 24 hours after completion of each exercise challenge. Participants will be
485 asked if they developed new symptoms and review guidance on the need to stop future exercise
486 challenges if any adverse events or new symptoms occurred per clinician judgement based on the
487 severity of symptoms.
488 10. The exercise challenge will end after 1 hour of the required activity is completed.

489 **5.2 Laboratory Testing**

490 **5.2.1 HbA1c**

491 HbA1c measurement will be performed locally at the Screening visit.

492 An additional blood sample will be obtained (venipuncture or fingerstick) and sent to the central
493 laboratory at the Control-IQ 1.5 Training visit and at the 13-week visit (or at early withdrawal of the
494 subject from the study providing they have completed at least 6 weeks of follow-up).

495 **5.2.2 Urine Pregnancy**

496 Urine pregnancy testing performed locally at clinical site for females of child-bearing potential at the
497 screening visit, at the start of study device use, and anytime pregnancy is suspected.

498

Chapter 6: Unanticipated Problem, Adverse Event, and

499

Device Issue Reporting

500

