295 The participant and companion if available will be instructed that if severe hypoglycemia occurs, the
296 study pump's insulin delivery should be suspended and glucagon administration if the participant is
297 unable to consume carbohydrate.

298 Participants will be required to have a home glucagon emergency kit. Participants who currently do not
299 have one will be given a prescription for the glucagon emergency kit.

300 **3.1.3 Training on Management of Hyperglycemia**

301 The t:slim X2 with Control-IQ system will issue a predictive hyperglycemia alert (Control-IQ High Alert)
302 when the system has increased insulin delivery, but detects a CGM value above 200 mg/dL and does not
303 predict the value will decrease in the next 30 minutes. During the course of the study, participants will be
304 permitted to change the CGM high glucose threshold alert setting on their device or mobile app, but will
305 be instructed to choose a value no greater than 300 mg/dL.

306 If the participant receives a Control-IQ High Alert, a prompt appears on the user interface to check the
307 site for occlusion and test blood glucose.

308 If a participant's CGM reading is >300 mg/dL for more than 60 minutes or is ≥ 400 mg/dL at any point,
309 the participant will be instructed to take the following steps:

- 310 • Perform a blood glucose meter check.
- 311 • If the blood glucose is >300 mg/dL, check for blood ketones with the study ketone meter.
- 312 • If the ketone level is ≥ 0.6 mmol/L (or ≥ 2.5 mmol/L at any time), take correction insulin, change
313 insulin (pump) infusion site and contact study staff. Continue to monitor their glucose and blood
314 ketone levels until they return to normoglycemia and ketones are < 0.6 mmol/l.
 - 315 ◆ If ketones are <0.6 mmol/l, they will be advised to continue to monitor their glucose until it
316 returns to normoglycemia and to repeat the ketone measurement in 90 minutes if necessary
- 317 • If correction insulin is administered via insulin syringe, turn Control-IQ off for four hours and until
318 glucose level has returned to <180 mg/dL.

319

320 **Special Considerations for Participants Taking SGLT-2 inhibitors, GLP-1 Receptor Agonists, or**
321 **DPP-IV Inhibitors**

322 Participants taking any SGLT-2 inhibitor will be instructed to perform scheduled ketone checks at least
323 twice a day (morning and evening) during the first two weeks of study device use, and at least once a day

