324 thereafter. If a participant taking an SGLT-2 inhibitor develop ketones > 0.6 on two successive occasions
325 during these 2 weeks (the first testing upon waking in a fasted state), they will be withdrawn from the
326 study.

327 For participants taking any SGLT-2 inhibitor, GLP-1 Receptor Agonist, or DPP-4 inhibitor, if a
328 participant's CGM reading is >250 mg/dL for more than 60 minutes or is ≥ 400 mg/dL at any point, the
329 participant will be instructed to take the following steps:

- 330 • Perform a blood glucose meter check.
- 331 • If the blood glucose is >250 mg/dL, check for blood ketones with the study ketone meter.
- 332 • If the ketone level is ≥ 0.6 mmol/L (or ≥ 2.5 mmol/L at any time), take correction insulin, change
333 insulin (pump) infusion site and contact study staff. Continue to monitor their glucose and blood
334 ketone levels until they return to normoglycemia and ketones are < 0.6 mmol/l.
 - 335 ◆ If ketones are <0.6 mmol/l, they will be advised to continue to monitor their glucose until it
336 returns to normoglycemia and to repeat the ketone measurement in 90 minutes if necessary
- 337 • If correction insulin is administered via insulin syringe, turn Control-IQ off for four hours and until
338 glucose level has returned to <180 mg/dL.

339

340 **3.1.4 Adjustments in Insulin Pump Settings**

341 Insulin and glucose data from the screening visit, as well as follow up visits, will be reviewed and the site
342 investigator may adjust insulin delivery profile settings as needed in accordance with their clinical
343 practice.

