- 574 • a hypoglycemic event occurred meeting the following definition of severe hypoglycemia: the event
575 required assistance of another person due to altered consciousness, and required another person to
576 actively administer carbohydrate, glucagon, or other resuscitative actions. This means that the
577 participant was impaired cognitively to the point that he/she was unable to treat himself/herself, was
578 unable to verbalize his/ her needs, was incoherent, disoriented, and/or combative, or experienced
579 seizure or loss of consciousness. These episodes may be associated with sufficient neuroglycopenia to
580 induce seizure or loss of consciousness. If glucose measurements are not available during such an
581 event, neurological recovery attributable to the restoration of glucose to normal is considered
582 sufficient evidence that the event was induced by a low glucose concentration.
- 583 • evaluation or treatment was obtained at a health care provider facility for an acute event involving
584 hypoglycemia, or the participant contacted the site and received guidance following the occurrence of
585 an acute event involving hypoglycemia

586 When a severe hypoglycemia event occurs (as defined above), an Adverse Event Form should be
587 completed. Severe hypoglycemia events should be considered to be serious adverse events with respect to
588 reporting requirements. When a severe hypoglycemia event occurs during use of a study device, it
589 generally will be considered to be unrelated to the device (per section 6.2.5) if the device functioned as
590 intended and there does not appear to be a flaw in how the device is intended to function.

591 **6.2.4 Hyperglycemic/Ketotic Events**

592 Hyperglycemia is only reportable as an adverse event when one of the following criteria is met:

- 593 • the event involved DKA, as defined by the Diabetes Control and Complications Trial (DCCT) and
594 described below
- 595 • evaluation or treatment was obtained at a health care provider facility for an acute event involving
596 hyperglycemia or ketosis, or the participant contacted the site and received guidance on how to
597 manage the hyperglycemia/ketosis
- 598 • blood ketone level ≥ 0.6 mmol/L, even if there was no communication with a health care provider at
599 the time of the event

600 Hyperglycemic events are classified as DKA if the following are present:

- 601 • Symptoms such as polyuria, polydipsia, nausea, or vomiting;

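### Meal-challenge item 5 bars a bolus in two symptom-free, ketone-positive situations where section 3.1.3, still in force, orders correction insulin

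*Combined protocol and SAP*

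**What the plan says.** Section 5.1.1, item 5, restricts insulin after each meal challenge: "Not give an additional bolus for up to 3 hours after the meal challenge, unless BG is above 300" "mg/dL for more than 1 hour, or symptoms of hyperglycemia develop". Sustained high glucose and symptoms are the only exceptions. Item 5 mentions neither ketones nor section 3.1.3.

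The parent section, 5.1, states: "Hyperglycemia and Hypoglycemia treatment guidelines (sections 3.1.3 and 3.1.2) remain in effect for the" challenges. It adds that participants go over them before each challenge.

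Section 3.1.3 has two sets of triggers.

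- **All participants.** Action starts when the "CGM reading is >300 mg/dL for more than 60 minutes or is" 400 mg/dL or higher, the latter with no minimum duration. A meter check follows and, if the meter is above 300, a ketone test.
- **Users of SGLT-2 inhibitors, GLP-1 receptor agonists or DPP-4 inhibitors.** Action starts when the "CGM reading is >250 mg/dL for more than 60 minutes or is" 400 mg/dL or higher, and the meter threshold for a ketone test is 250.

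The next step is the same in both sets: "If the ketone level is ≥ 0.6 mmol/L (or ≥ 2.5 mmol/L at any time), take correction insulin, change" the infusion site and contact study staff. Neither set requires symptoms. Section 7.3 lets users of these drugs take part if the dose has been stable for 3 months.

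**The concern.** Item 5 carries its own exception list. That list closely matches one arm of section 3.1.3 (above 300 mg/dL for more than an hour). It omits the 400 mg/dL arm, the lower threshold for users of the three drug classes, and the ketone result. A participant in one of the omitted situations has two written instructions that point in opposite directions, and following item 5 literally delays insulin that the safety guideline orders.

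The setting makes this worth settling. One challenge meal has no bolus and one has half the calculated bolus, each with at least 50 g of carbohydrate, so hyperglycemia is foreseeable. A care partner must be present, but section 5.1 does not require study staff to be. Section 3.1.3 deliberately gives users of the three drug classes a lower action threshold, and section 6.2.4 notes that ketoacidosis can occur below 250 mg/dL and may be more common with SGLT-2 inhibitors. The protocol also treats this ketone level as notable elsewhere: under section 6.2.4, a hyperglycemic event is reportable at a blood ketone level of at least "0.6 mmol/L, even if there was no communication with a health care provider at" the time.

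**Working it through.** The plan gives no figure to reproduce, so the check sets rule against rule, with no symptoms unless stated.

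**Rules**

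- Item 5 permits a bolus if BG is above 300 mg/dL for more than 1 hour, or if there are symptoms.
- Section 3.1.3, all participants, orders insulin if (CGM above 300 for more than 60 min, or CGM at least 400), and meter above 300, and ketones at least 0.6 mmol/L.
- Section 3.1.3, users of the three drug classes, orders insulin if (CGM above 250 for more than 60 min, or CGM at least 400), and meter above 250, and ketones at least 0.6 mmol/L.

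**Test cases**

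| Case | State | 3.1.3 | Item 5 | Conflict |
|---|---|---|---|---|
| A | Any participant; CGM reaches 400 after 40 min above 300; meter 380; ketones 0.7 | orders insulin | forbids bolus | yes |
| B | SGLT-2 user; CGM 270 for 75 min; meter 265; ketones 0.7 | orders insulin | forbids bolus | yes |
| C | As B, ketones 0.5 | no insulin order | forbids bolus | no |
| D | As B, with symptoms | orders insulin | permits bolus | no |
| E | CGM and meter above 300 for 75 min; ketones 0.7 | orders insulin | permits bolus | no |

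Cases A and B give the two situations. Item 5 does not say whether BG means the meter or the CGM value, but the result is the same either way: in A neither has been above 300 for more than an hour, and in B neither exceeds 300. A grid over CGM, meter value, duration, ketones and drug use, symptom-free throughout, found the same two situations. It found a third only if the 2.5 mmol/L clause in section 3.1.3 is read as a stand-alone trigger. The point does not rely on that reading.

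**How far glucose must rise.** Item 2 of section 5.1.1 says: "Only begin the meal challenge if CGM glucose is between 70 mg/dL and 200 mg/dL".

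- Situation 1: 400 − 200 = a rise of at least 200 mg/dL.
- Situation 2: 250 − 200 = a rise of more than 50 mg/dL, held above 250 for more than 60 minutes.

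**How long a conflict can last**

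- Situation 1: if BG stays above 300, item 5's own exception opens after 60 minutes, so the conflict lasts at most about 60 minutes from crossing 300. In case A that leaves 60 − 40 = 20 minutes.
- Situation 2: taking the restriction as 3 hours from the end of the meal, and 250 as crossed at meal end or later, at most about 3 − 1 = 2 hours remain.

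These are conditional upper limits. Actual durations cannot be computed from the documents.

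**Exposure.** With 30 completers doing all three meals, 30 × 3 = 90 meal challenges fall under both rules, and 30 × 2 = 60 of them have no bolus or a half bolus. These counts are exposure, not a frequency of conflict. Situation 2 applies only to users of the three drug classes, whose number is not given.

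**The case against.** The strongest answer is that section 5.1 already settles the matter. It governs 5.1.1, keeps section 3.1.3 in force without a carve-out, and requires review before every challenge. Section 3.1.3 also has a dedicated block for users of the three drug classes, so for situation 2 it is arguably the more specific rule. This makes priority of 3.1.3 the sensible reading, but it remains an inference. Item 5 is the rule written for this period, has a narrower exception list and does not point to 3.1.3. Under the deviation definition in section 9.4, a participant in either situation breaches one rule or the other.

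Several points reduce the weight and stand:

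- Item 5 restricts boluses the participant gives. The closed loop goes on adjusting delivery, so what is delayed is a user-given correction, not all added insulin.
- The time limits shown above apply.
- A trained care partner is present, and 3.1.3 also says to contact staff.
- Section 6.2.4 sets a reporting threshold. It does not by itself show that insulin is needed.
- Participants receive the guidelines in the Study Participant Instruction Sheet, which is not among the documents and may already resolve the point.

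A further argument is that correction insulin could be given by syringe and so not count as a bolus. Section 3.1.3 mentions a syringe only conditionally and does not prescribe it, so this does not remove the conflict.

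**Conclusion.** The concern holds, as a minor one. The protocol text gives opposite instructions in two definable situations, both symptom-free with ketones of at least 0.6 mmol/L, and does not state which rule prevails. The conclusion rests on reading item 5 as written and covers the protocol text only. Confidence in the conflict itself is high; how often it would arise is unknown. No endpoint or analysis changes.

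**What to change.** In section 5.1.1 item 5, after the symptom exception, add: *or section 3.1.3 calls for correction insulin; section 3.1.3 takes precedence*. Carry the same wording into the Study Participant Instruction Sheet.

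The cost is one clause and a matching edit, with no added procedures. The downside is that some challenges may be interrupted by correction insulin; how many cannot be estimated from the documents. Those would be challenges in which section 3.1.3 already directs the participant to take it.
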